9.7.1.8 Safety Analyses

Evaluations of safety will be performed on the Safety Analysis Set. The incidence of AEs (including changes from baseline in physical and neurological examinations, and dermatological assessments), out-of-normal-range laboratory safety test variables, abnormal ECG findings, out-of-range vital signs, suicidality (C-SSRS), and results of the sleep questionnaire, along with the change from baseline in laboratory safety test variables, ECGs, safety MRI, and vital sign measurements will be summarized by treatment group using descriptive statistics.

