The PK/PD modeling described above, which was conducted using data obtained from healthy volunteers, has also been supported by modeling of data from subjects with an underlying AD pathology (Study 101). Furthermore, external data with another BACE1 inhibitor (MK-8931) showed a similar PD effect in AD patients as in healthy volunteers (Forman, et al., 2013). Therefore we are confident that the modeling of E2609 effects in healthy subjects will be applicable for both MCI/Prodromal and Mild AD dementia patients.

The exposure of the highest dose in this study (50 mg QD tablet administered with food) is less than that of the 100 mg QD dose (capsule administered fasted) in Study 002.

The 100 mg QD dose administered for 14 days in Study 002 was well tolerated with no clinically significant changes in laboratory parameters, vital signs, or ECG parameters. On Day 15, for the 100 mg QD cohort in Study 002, there was a reduction of CD4 lymphocyte counts compared with placebo (CD4 lymphocyte counts on E2609 decreased by 3.1% from baseline, whereas the placebo control showed an increase of 8.7%), but this decrease was less than that observed at doses of 200 mg (22.9% decrease) or 400 mg (17.3% decrease). No subjects had infections or drug rash while receiving E2609 100 mg QD or at lower doses in Study 002, whereas at 200 mg and 400 mg QD, 4 subjects had symptomatic orolabial HSV1 relapses and 2 subjects at the highest dose had drug rash. The highest dose for Study 202 of 50 mg QD (tablet administered with food) is therefore expected to have a similar or better safety profile compared with the 100 mg QD capsule (administered fasted) in Study 002. Specific exclusion criteria, blinded and unblinded safety monitoring procedures, and safety criteria for discontinuation from study drug are included in this study in order to mitigate any immunology-related risk with E2609, particularly in light of the progression from 14 days of dosing (Study 002) to 18 months of dosing in this study.

Subjects in the MCI/Prodromal cohort, whether in Stage A or Stage B, will be randomized to receive either placebo or E2609 at 5 mg, 15 mg, or 50 mg QD. Subjects with mild AD (Stage B) will be randomized to receive either placebo or E2609 at 15 mg or 50 mg QD, but not the 5-mg QD dose. The rationale for not including an E2609 5-mg QD dose in the dose regimens for subjects with mild AD is that more advanced disease may require greater reduction in CSF $A\beta$ levels for comparable effects.

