9.7.1.2 Definitions of Analysis Sets

- The Randomized Set is the group of subjects who are randomized to study drug.
- The Safety Analysis Set is the group of subjects who receive at least 1 dose of study drug and have at least 1 postdose safety assessment.
- The Full Analysis Set (FAS) is the group of randomized subjects who receive at least 1 dose of study drug and have baseline and at least 1 postdose primary efficacy measurement.
- The Per Protocol (PP) Analysis Set is the subset of subjects in the FAS who sufficiently comply with the protocol. The PP Analysis Set will be used to conduct a sensitivity analysis of the primary efficacy endpoint. Details of the evaluability criteria will be determined before database lock and treatment unblinding, and will be specified in the statistical analysis plan.
- The PK Analysis Set is the group of subjects with at least 1 quantifiable E2609 plasma concentration accompanied by a documented dosing history.
- The PD Analysis Set is the group of subjects who have a baseline PD measurement and at least 1 posttreatment PD measurement.

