9.7.1.8.2 ADVERSE EVENTS

The AE verbatim descriptions (investigator terms from the eCRF) will be classified into standardized medical terminology using the Medical Dictionary for Regulatory Activities (MedDRA). Adverse events will be coded to the MedDRA (Version 17.0 or higher) lower level term closest to the verbatim term. The linked MedDRA preferred term and primary system organ class (SOC) are also captured in the database.

A TEAE is defined as an AE that emerges during treatment, having been absent at pretreatment (Baseline) or

- Reemerges during treatment, having been present at pretreatment (Baseline) but stopped before treatment, or
- Worsens in severity during treatment relative to the pretreatment state, when the AE is continuous.

Only those AEs that are treatment-emergent will be included in summary tables. All AEs, treatment-emergent or otherwise, will be presented in subject data listings.

The TEAEs will be summarized by treatment group on the Safety Analysis Set. The incidence of TEAEs will be reported as the number (percentage) of subjects with TEAEs by SOC and preferred term. A subject will be counted only once within an SOC and preferred term, even if the subject experienced more than 1 TEAE within a specific SOC and preferred term. The number (percentage) of subjects with TEAEs will also be summarized by maximum severity (mild, moderate, or severe). The number (percentage) of subjects with TEAEs will also be summarized by relationship to study drug (Yes [related] and No [not related]).

The number (percentage) of subjects with treatment-related TEAEs will be summarized by SOC and preferred term. Treatment-related TEAEs include those events considered by the investigator to be related to study drug. The number (percentage) of subjects with treatment-related TEAEs will also be summarized by maximum severity (mild, moderate, or severe).

Adverse events will be summarized by the following subgroups: *ApoE4* status (positive or negative), prior treatment with AChEIs or memantine (no or yes), and clinical subpopulation (MCI/Prodromal or mild AD).

The number (percentage) of subjects with TEAEs leading to death will be summarized by MedDRA SOC and preferred term for each treatment group. A subject data listing of all AEs leading to death will be provided.

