9.7.1.8.3 LABORATORY VALUES

Laboratory results will be summarized using International System of Units, as appropriate. For all quantitative parameters listed in [Section 9.5.1.5.3](#), the actual value and the change from baseline to each postbaseline visit and to the end of treatment (defined as the last on-treatment value) will be summarized by visit and treatment group using descriptive statistics. Qualitative parameters listed in [Section 9.5.1.5.3](#) will be summarized using frequencies (number and percentage of subjects), and changes from baseline to each postbaseline visit and to end of treatment will be reported using shift tables. Percentages will be based on the number of subjects with both nonmissing baseline and relevant postbaseline results.

Laboratory test results will be assigned a low/normal/high (LNH) classification according to whether the value was below (L), within (N), or above (H) the laboratory parameter's reference range. Within-treatment comparisons for each laboratory parameter will be based on 3-by-3 tables (shift tables) that compare the baseline LNH classification to the LNH classification at each postbaseline visit and at the end of treatment. Similar shift tables will also compare the baseline LNH classification to the LNH classification for the highest and lowest value during the treatment period.

[Appendix 1](#) (Sponsor's Grading for Laboratory Values) presents the criteria that will be used to identify subjects with treatment-emergent markedly abnormal laboratory values (TEMAVs). Except for phosphate, a TEMAV is defined as a postbaseline value with an increase from baseline to a Grade of 2 or higher. For phosphate, a TEMAV was defined as a postbaseline value with an increase from baseline to a Grade of 3 or higher. When displaying the incidence of TEMAVs, each subject may be counted once in the laboratory parameter high and in the laboratory parameter low categories, as applicable.

Lymphocyte subsets (ie, CD4 [T helper cells], CD8 [cytotoxic T cells], CD19 [B cells], CD16/CD56 [natural killer cells] and CD14 [macrophages]) and regulatory T cells will be summarized in the same manner as other laboratory parameters. Mean lymphocyte subsets and the mean change from baseline in lymphocyte subsets will also be displayed graphically over time by dose.

Serum IgG, IgM, and IgA will be measured and summarized in the same manner as other laboratory parameters.

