9.7.4 Other Statistical/Analytical Issues

Adaptive Randomization in the MCI/Prodromal Cohort

Randomization to placebo or 1 of 3 dose groups of E2609 will be fixed for the first 100 subjects randomized in the study (1:1:1:1; placebo to each of the 3 active doses). Randomization probabilities to each treatment group will be updated at each interim analysis, such that the randomization probability will be increased for the placebo group and dosage groups that represent the potential target dose (ED₉₀), and simultaneously decreased for other active arms.

Within the 2 clinical populations (MCI/Prodromal and mild AD), subjects will be stratified at randomization by *ApoE4* status (positive or negative) and prior treatment with AChEIs or memantine or both (yes or no).

Subjects with mild AD will be randomized to placebo or 1 of 2 dose groups of E2609.

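### Safety tables other than adverse events have no cohort split, although the cohort mix differs by arm, so pooled dose-versus-placebo contrasts are not randomised comparisons

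*Protocol*

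**What the plan says.** Section 9.7.1.2 defines the Safety Analysis Set as the "group of subjects who receive at least 1 dose of study drug and have at least 1 postdose safety assessment", with no reference to cohort. Section 9.7.1.8 states that safety results "will be summarized by treatment group using descriptive statistics".

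For adverse events, section 9.7.1.8.2 says: "The incidence of TEAEs will be reported as the number (percentage) of subjects with TEAEs by SOC and preferred term". The same section adds subgroup summaries by ApoE4 status, "prior treatment with AChEIs or memantine (no or yes), and clinical subpopulation (MCI/Prodromal or mild AD").

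The sections on laboratory values, vital signs and ECGs (9.7.1.8.3 to 9.7.1.8.5) name treatment group, and visit where relevant, but no subpopulation. For lymphocyte subsets the plan is: "Mean lymphocyte subsets and the mean change from baseline in lymphocyte subsets will also be displayed graphically over time by dose". Safety MRI and C-SSRS appear only in the general sentence of 9.7.1.8, again by treatment group.

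The two cohorts do not share an allocation scheme. Under section 9.4.4 mild AD subjects "will be randomized to receive either placebo or E2609 at 15 mg or 50 mg QD, but not the 5-mg QD dose", and section 9.1 fixes their ratio at 1:1:1. MCI/Prodromal subjects go to four arms, equally for the first 100. After that, under section 9.7.4, "the randomization probability will be increased for the placebo group and dosage groups that represent the potential target dose".

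**The concern.** A column headed by treatment group on this set combines two separately randomised populations in proportions that depend on the arm. The 5 mg column holds MCI/Prodromal subjects only. The placebo, 15 mg and 50 mg columns hold both, in shares that shift as adaptation moves MCI/Prodromal subjects between arms. If the cohorts differ in background rates, or in how a measurement drifts from baseline, the pooled columns differ with no drug effect.

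Safety and tolerability, with immunological and haematological parameters named, is the second primary objective (section 8.1). Section 7.1 reports lymphocyte reductions at higher doses in the multiple-dose study, and section 7 says the results will guide the choice of doses for Phase 3. Lymphocyte data are among those without a cohort split. Section 9.2.3 itself argues that the cohorts should be analysed separately so that mild AD data do not confound the MCI/Prodromal results.

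**Working it through.** The protocol states no power or error rate for safety, so there is no figure to reproduce. The check asks how large an artefact pooling can create when the drug does nothing.

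**Inputs from the protocol.** MCI/Prodromal: 60 + 440 = 500 subjects, four arms. Mild AD: about 200 at 1:1:1 over placebo, 15 mg and 50 mg, so 200/3 = 66.7 per arm and 0 on 5 mg.

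**Assumed inputs.** Background event rates of 10% in MCI/Prodromal and 15% or 20% in mild AD; the adaptive split shown below.

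**Step 1, cohort mix.** Share of mild AD in an arm: f = n_mild / (n_mild + n_MCI).

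- Equal MCI/Prodromal allocation, 125 per arm: f = 66.7 / 191.7 = 34.8% on placebo, 15 mg and 50 mg; 0% on 5 mg.
- Illustrative adaptive split (placebo 165, favoured dose 205, other doses 65 each), with 15 or 50 mg favoured: placebo 66.7 / 231.7 = 28.8%; favoured dose 66.7 / 271.7 = 24.5%; the other of 15 and 50 mg 66.7 / 131.7 = 50.6%; 5 mg 0%.

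**Step 2, spurious difference from placebo.** Crude arm rate = p_MCI(1 − f) + p_mild × f, so the difference from placebo is (f_arm − f_placebo)(p_mild − p_MCI).

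| Split | Arm | 10% vs 15% | 10% vs 20% |
|---|---|---|---|
| Equal | 5 mg | −1.7 points | −3.5 points |
| Equal | 15 and 50 mg | 0 | 0 |
| Adaptive | 5 mg | −1.4 | −2.9 |
| Adaptive | favoured 15 or 50 mg | −0.2 | −0.4 |
| Adaptive | non-favoured 15 or 50 mg | +1.1 | +2.2 |

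Within a cohort, or stratified by cohort, every entry is 0.

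**Step 3, outcomes without a split.** Treatment-emergent markedly abnormal laboratory values and the QTcF categories are percentages of subjects, so Step 2 applies directly. For mean change from baseline the same algebra gives (f_arm − f_placebo) times the difference between cohorts in drug-free change. Under equal allocation, 5 mg against placebo carries −0.348 of that difference. Under the adaptive split, the non-favoured dose carries 0.506 − 0.288 = +0.218 of it. The protocol gives no value for the difference.

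**Step 4, follow-up.** Planned treatment is 78 weeks in every arm, and section 9.7.3 keeps randomised subjects on the full 18 months after early success. Only a futility stop truncates treatment by enrolment date. The assumptions are: stop at 300 randomised; 6 per month in Stage A, a 6-month pause, then 15 to 25 per month; after the first 100, 35% to placebo, 45% to the favoured dose and 10% to each other dose; constant hazard 0.02 per month, with incidence 1 − exp(−0.02 × months).

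| Arm | Mean months on treatment (15 / 25 per month) | Crude incidence (15 / 25 per month) |
|---|---|---|
| Placebo | 9.3 / 6.7 | 16.4% / 12.0% |
| Favoured dose | 8.8 / 6.2 | 15.7% / 11.2% |
| Other doses | 12.2 / 9.6 | 21.1% / 16.9% |

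These differences arise inside the MCI/Prodromal cohort, so a cohort split does not remove them.

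**The case against.** Four arguments count against the point.

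- **Pooling is inferred.** No sentence specifies pooled columns. Section 9.1 gives each cohort its own placebo group, and section 9.2.3 says the cohorts are analysed independently for decision making. However, section 9.7.1.4 lists clinical subpopulation as a baseline variable to be tabulated within treatment group on the Safety Analysis Set, and 9.7.1.8.2 treats it as a subgroup. Both make sense only if the treatment-group columns hold both cohorts.
- **Adverse events are already covered.** This stands. A reader might infer that dose differences in the drug's known harms generally are confounded. Infection, herpes, rash and discontinuation due to adverse events are all adverse events, and these are summarised by subpopulation. The MRI features that end treatment must also be reported as adverse events, as must marked QTc prolongation. The gap is in laboratory, ECG, vital-sign, MRI and C-SSRS summaries.
- **The artefact is small and the summaries are descriptive.** For 5 mg against placebo at 10% and 13.5%, the standard error is √(0.10 × 0.90/125 + 0.135 × 0.865/191.7) = 3.6 points, so the 3.5-point artefact is about one standard error. No test is planned that it could make falsely positive. That limits the severity, but the artefact is systematic and avoidable.
- **The SAP may settle it.** It may. But the protocol positively names the set and the grouping, and grants the split to one class of data only. Aligning the rest is a correction to stated text.

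**Conclusion.** The point holds in a limited form. For safety data other than adverse events, the stated grouping mixes cohorts, and a pooled dose-versus-placebo contrast is not a randomised comparison. The clear case is 5 mg, with 0% mild AD against about 35% on placebo under equal MCI/Prodromal allocation. There the illustrative artefact is 1.7 to 3.5 points in favour of 5 mg. The shares follow from the planned sample sizes. The points rest on assumed event rates, and there is no artefact if the cohorts do not differ in background rates or changes.

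Two stronger readings are not supported. A reader might infer that the 15 and 50 mg contrasts are distorted by design; under equal MCI/Prodromal allocation they are not, and any distortion depends on how far adaptation moves the split. A reader might also infer that follow-up differs between arms by design. Planned follow-up is equal, and section 9.7.1.8.1 tabulates exposure by treatment group. Systematic truncation by enrolment date arises only after a futility stop.

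**What to change.** In section 9.7.1.8, state that all safety tables and figures are presented by treatment group within cohort, as randomised. Extend the existing adverse-event split to laboratory values (including lymphocyte subsets and markedly abnormal values), ECG, vital signs, safety MRI and C-SSRS. Where a combined figure is also shown, stratify the dose-versus-placebo comparison by cohort, and compare 5 mg with MCI/Prodromal placebo only. Add that, if a futility stop truncates treatment, event rates per person-time at risk accompany the crude percentages.

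The cost is a few sentences and more tables from data already collected, with smaller groups in each table. No assessment, visit or clinical rule changes.

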9.7.1.8.1 EXTENT OF EXPOSURE

The extent of exposure to study drug will be summarized as cumulative extent of exposure in 3-month intervals. The number and percent of subjects will be presented by treatment group.

Duration of exposure will be summarized using descriptive statistics in 3-month intervals. The number and percent of subjects will be presented by treatment group.

9.7.1.8.2 ADVERSE EVENTS

The AE verbatim descriptions (investigator terms from the eCRF) will be classified into standardized medical terminology using the Medical Dictionary for Regulatory Activities (MedDRA). Adverse events will be coded to the MedDRA (Version 17.0 or higher) lower level term closest to the verbatim term. The linked MedDRA preferred term and primary system organ class (SOC) are also captured in the database.

A TEAE is defined as an AE that emerges during treatment, having been absent at pretreatment (Baseline) or

- Reemerges during treatment, having been present at pretreatment (Baseline) but stopped before treatment, or
- Worsens in severity during treatment relative to the pretreatment state, when the AE is continuous.

Only those AEs that are treatment-emergent will be included in summary tables. All AEs, treatment-emergent or otherwise, will be presented in subject data listings.

The TEAEs will be summarized by treatment group on the Safety Analysis Set. The incidence of TEAEs will be reported as the number (percentage) of subjects with TEAEs by SOC and preferred term. A subject will be counted only once within an SOC and preferred term, even if the subject experienced more than 1 TEAE within a specific SOC and preferred term. The number (percentage) of subjects with TEAEs will also be summarized by maximum severity (mild, moderate, or severe). The number (percentage) of subjects with TEAEs will also be summarized by relationship to study drug (Yes [related] and No [not related]).

The number (percentage) of subjects with treatment-related TEAEs will be summarized by SOC and preferred term. Treatment-related TEAEs include those events considered by the investigator to be related to study drug. The number (percentage) of subjects with treatment-related TEAEs will also be summarized by maximum severity (mild, moderate, or severe).

Adverse events will be summarized by the following subgroups: *ApoE4* status (positive or negative), prior treatment with AChEIs or memantine (no or yes), and clinical subpopulation (MCI/Prodromal or mild AD).

The number (percentage) of subjects with TEAEs leading to death will be summarized by MedDRA SOC and preferred term for each treatment group. A subject data listing of all AEs leading to death will be provided.

The number (percentage) of subjects with treatment-emergent SAEs will be summarized by MedDRA SOC and preferred term for each treatment group. A subject data listing of all SAEs will be provided.

The number (percentage) of subjects with TEAEs leading to discontinuation from study drug will be summarized by MedDRA SOC and preferred term for each treatment group. A subject data listing of all AEs leading to discontinuation from study drug will be provided.

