9.5.1.5.1 ADVERSE EVENTS AND EVENTS ASSOCIATED WITH SPECIAL SITUATIONS

An AE is any untoward medical occurrence in a subject or clinical investigation subject administered an investigational product. An AE does not necessarily have a causal relationship with the medicinal product. For this study, the study drug is E2609.

The criteria for identifying AEs in this study are:

- Any unfavorable and unintended sign (including an abnormal laboratory finding), symptom, or disease temporally associated with the use of an investigational product, whether or not considered related to the investigational product (Note: It is not necessary to report every sign or symptom as a separate AE if the overall disease [diagnosis] is being reported as an AE.)
- Any new disease or exacerbation of an existing disease
- Any deterioration in nonprotocol-required measurements of a laboratory value or other clinical test (eg, ECG or x-ray) that results in symptoms, a change in treatment, or discontinuation of study drug
- Recurrence of an intermittent medical condition (eg, headache) not present pretreatment (Baseline)
- An abnormal laboratory test result should be considered an AE if the identified laboratory abnormality leads to any type of intervention, discontinuation of study drug, or withholding of study drug, whether prescribed in the protocol or not

All AEs observed during the study will be reported on the eCRF. All AEs, regardless of relationship to study drug or procedure, should be collected beginning from the time the subject signs the study ICF through the last visit (Visit 20, as shown in [Table 7](#)). For subjects who discontinue early from study drug but undertake further efficacy assessments, AEs will only be collected for 3 months after the last dose of study drug, ie, through to the second follow-up visit (Visit 20). Subjects who fail screening primarily due to AE(s) must have the AE(s) leading to screen failure reported on the Screening Disposition eCRF. SAEs will be collected for 3 months after the last dose of study drug, ie, through to the second follow-up visit (Visit 20). For subjects who discontinue early from study drug but continue with further efficacy assessments, SAEs will be solicited only for 3 months after the last dose of study drug, i.e. up to the 2nd follow up visit (Visit 20). However, any SAEs volunteered by subjects after this time point must be reported according to standard procedures.

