by time interaction in the statistical analysis. There was evidence that the lower doses of 50 to 100 mg also caused some reduction in CD4 lymphocyte counts by Day 15. Doses above 100 mg appeared to be associated with greater reductions in CD4 and CD8 lymphocyte counts, which occurred earlier in the treatment period compared with the effects of 25 to 100 mg doses. These effects on lymphocyte counts gradually resolved from Day 20 to Day 35, which were 6 and 21 days, respectively, after administration of the last dose of E2609 on Day 14. Reductions in CD4 and CD8 lymphocyte counts at doses of 200 and 400 mg to a level close to or less than the lower limit of normal (LLN) could be associated with increased risk of developing relapse of orolabial herpes or other infections.

In Study 003, a drug-drug interaction study, PK results showed that itraconazole (a potent inhibitor of cytochrome P450 [CYP] 3A4 and carboxyesterase-2 [CES2]) caused a mild increase (by approximately 70%) of the area under the concentration x time curve (AUC) of E2609. Rifampin (a potent CYP3A4 inducer) caused a mild decrease (by approximately 20%) of the AUC of E2609. Donepezil (a moderate CES2 inhibitor) caused a mild increase (by approximately 20%) of the AUC of E2609 when coadministered with E2609 but not when dosed at least 2 hours apart from E2609. E2609 (which inhibits the P-glycoprotein 1 transporter) did not affect the PK properties of digoxin. Nonclinical studies also indicated that other CYP pathways apart from CYP3A4 would not be major pathways of metabolism of E2609. Based on these results, it is not considered necessary to impose restrictions during E2609 treatment on the use of concomitant medications that may be CYP3A4 inhibitors or other CYP enzymes inhibitors, or CES2 inhibitors. Similarly, it was also not considered necessary to restrict the use of concomitant medications which are inducers of CYP450 enzymes.

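### As written, new AEs, SAEs and fatal AEs with onset in the 12-week off-treatment follow-up enter no planned by-arm AE table, only listings

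*Protocol*

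**What the plan says.** Section 9.7.1.8.2 of the protocol defines a treatment-emergent event in three limbs. The first reads "A TEAE is defined as an AE that emerges during treatment, having been absent at pretreatment (Baseline"). The second covers events that had stopped before treatment and come back during it. The third is "Worsens in severity during treatment relative to the pretreatment state, when the AE is continuous". None of the three gives a number of days after the last dose.

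The section then sets the tabulation rule: "Only those AEs that are treatment-emergent will be included in summary tables". Everything else is sent elsewhere: "All AEs, treatment-emergent or otherwise, will be presented in subject data listings". Serious events follow the same pattern: "The number (percentage) of subjects with treatment-emergent SAEs will be summarized by MedDRA SOC and preferred term for each treatment group", next to "A subject data listing of all SAEs will be provided". The death table counts TEAEs leading to death, and the full set of AEs leading to death is a listing.

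Section 9.5.1.5.1 fixes a longer collection window. AEs "should be collected beginning from the time the subject signs the study ICF through the last visit (Visit 20"), and SAEs are collected for the same 3 months after the last dose. Section 9.1.2 divides the Randomization Phase into a 78-week Treatment Period and a 12-week Follow-Up Period after the last dose. Section 9.2.6 describes the two follow-up visits as off-treatment.

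**The concern.** The protocol collects AEs for 12 weeks off drug and then writes a rule that keeps new events from that period out of every AE, SAE and death table. Safety and tolerability, with immunological and hematological parameters named, is a primary objective (section 8.1). Section 9.2.6 lists the off-treatment visits among the measures that mitigate the step from 14 days to 18 months of dosing. Section 7.1 reports that lymphocyte effects in the multiple-dose study resolved gradually between two days "which were 6 and 21 days, respectively, after administration of the last dose of E2609".

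An infection, rash or serious event that starts shortly after the drug is stopped is therefore of interest for this compound. Under the rule it would have to be found by reading listings, with no count or percentage by arm.

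**Working it through.** No sample size, power or error rate depends on this point, so the check is mainly a comparison of sections.

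1. **What counts as treatment-emergent.** All three limbs in 9.7.1.8.2 require the event to emerge, re-emerge or worsen during treatment.

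2. **Does treatment include follow-up?** Section 9.1.2 names Treatment and Follow-Up as separate periods, and 9.2.6 calls the follow-up visits off-treatment. Section 9.7.1.8.3 defines end of treatment for laboratory values by the last on-treatment value. The natural reading is that follow-up lies outside treatment.

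3. **What is tabulated.** AE, SAE and death tables are all limited to treatment-emergent events. The opening of 9.7.1.8 speaks of AE incidence by treatment group in general terms, but the specific rule in 9.7.1.8.2 narrows it.

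4. **What is collected.** AEs run from consent to Visit 20 and SAEs to 3 months after the last dose (9.5.1.5.1, 9.5.4.1).

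5. **The difference between 3 and 4.** Events with first onset, or first worsening, after the last dose and up to Visit 20 are collected and listed but not tabulated by arm.

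**Size in time.** Inputs: 78 weeks of treatment and 12 weeks of follow-up (9.1.2). Table 7 agrees: Visit 18 is Day 547 and Visit 20 is Day 631, so 631 − 547 = 84 days = 12 weeks.

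- Completer: 12 / (78 + 12) = 12/90 = 13.3% of collection time after first dose.
- Subject who stops drug at week t: 12 / (t + 12). With t = 12, chosen only for illustration, 12/24 = 50%.

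These are shares of time. The protocol gives no rate from which a number of events could be derived.

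**What the rule leaves intact.**

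- An AE that starts on drug and later proves fatal is still a TEAE leading to death.
- The infection, rash or other AE that causes a subject to stop arises on drug. It is counted as a TEAE and again among TEAEs leading to discontinuation.
- Lymphocyte subsets and immunoglobulins are scheduled at follow-up: Visit 19, with Visit 20 conditional on the Visit 19 result in Table 7. Under 9.7.1.8.3 they are summarized by visit and treatment group at each postbaseline visit.

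**The case against.** The strongest reply is that the TEAE sentence gives no end date. Where the protocol means to cut at the last dose it says so, as it does for concomitant medications in 9.7.1.5. Section 9.7.1.8.3 also calls laboratory values treatment-emergent merely because they worsen after baseline. On this view the post-dose window is an operational detail for the SAP, to which 9.7.1 defers further detail.

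Part of this stands: an SAP could supply a window, and the term is not used uniformly. But the protocol does more than leave the window open. It pairs a definition tied to treatment with an exclusive tabulation rule, in a document that separates treatment from follow-up. An SAP that tabulated follow-up events would be departing from that wording.

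The reply is stronger against larger claims that a reader might infer.

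- **That post-dose safety is never compared between arms.** The documents do not support this. Laboratory data at follow-up are summarized by arm, safety MRI (scheduled at Visit 20) is summarized by treatment group, and the DSMB reviews all safety data unblinded (9.1).
- **That the whole window of known pharmacological effect is lost.** The documented effect is on lymphocyte counts, and those are tabulated off drug. The clearest reductions were at 200 and 400 mg, with some CD4 reduction at 50 to 100 mg (7.1). Section 9.4.4 reports no infection or drug rash at or below 100 mg in that study. The top dose here is 50 mg, although given for 18 months rather than 14 days.
- **That the tables are biased toward no difference because higher doses stop earlier.** No figure shows that early stopping, or post-dose events, will differ by dose.

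It is also fair to say that folding 12 off-drug weeks into the main TEAE rate could dilute an on-drug difference. The fix has to respect that.

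**Conclusion.** The point holds in limited form. Followed as written, 9.7.1.8.2 gives listings but no by-arm AE, SAE or death table for events that first appear or worsen in the 12-week Follow-Up Period, although those events are collected.

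The affected span is 12 of 90 weeks for a completer and a larger share for a subject who stops early. How many events this concerns, and whether the number differs by dose, cannot be determined from the protocol. The 13% must not be read as a share of events missed.

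The conclusion rests on reading treatment as excluding the named Follow-Up Period, which the protocol's own period definitions support. It does not rest on any assumed bias between doses. This is a reporting gap in a primary safety objective that is cheap to close. It does not invalidate the on-treatment comparison.

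**What to change.** Amend section 9.7.1.8.2 as follows.

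- Keep the on-treatment TEAE tables as the main display.
- Add by-arm tables of AEs, SAEs and AEs leading to death with onset or worsening after the last dose through Visit 20, shown separately from the on-treatment TEAEs.
- For SAEs and deaths, also give a combined by-arm count from first dose through Visit 20.
- Delete the sentence that limits summary tables to treatment-emergent AEs, or qualify it so that these tables are allowed.

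The cost is a short text change and a few more tables, with no new data collection. The combined counts will include some background events that occurred off drug, so the on-treatment and post-treatment parts should stay visible beside them.
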